Protocol & Statistical Analysis Plan

Official Title: Influence of Exercise on Neurocognitive Function in Breast Cancer

NCT02793921

Document Date: 6/14/2023

Title of study:

Exercise Program in Cancer and Cognition (EPICC)

Brief description:

This is a single-site randomized control trial to test whether a moderate-intensity aerobic exercise intervention can prevent cognitive decline in postmenopausal women with breast cancer. Women who meet the eligibility criteria will be randomly assigned to either receive the intervention or usual care. Data will be collected prior to initiating endocrine therapy for breast cancer (TP1) and approximately 7 months later (TP2) and include fitness testing and a battery of neuropsychic tests, blood biomarkers, and other behavioral measures; a subset of women will undergo MR imaging. For women who agree to additional follow-up, data will also be collected approximately 12 months post TP1 (TP3).

Specific aims:

We will examine whether a well-controlled and monitored site-based exercise intervention improves cognitive function in postmenopausal women with early stage breast cancer. 1. Compared to usual care, examine whether the 6-month exercise intervention improves cognitive function in postmenopausal women with early stage breast cancer. Hypothesis 1. Exercise will improve cognitive function in women receiving AI therapy in a domain specific fashion such that attention, executive and memory functions will be influenced more than other domains.

2. Compared to usual care, examine the direct effects of exercise on neuroimaging metrics of brain health including regional gray matter volume, white matter architecture and functional dynamics of the brain and the pro-inflammatory biomarkers (IL-6, TNF- α), and explore the direct effects of exercise on symptoms (fatigue, sleep problems, depression, anxiety). Hypothesis 2. Exercise will improve neuroimaging metrics of brain health and pro-inflammatory biomarkers.

3. Compared to usual care, explore whether the effects of exercise on cognitive function are mediated by a) neuroimaging metrics of cognitive function, b) IL-6 and TNF- α levels, c) symptoms (fatigue, sleep problems, depression, anxiety), d) and moderated by E2 levels over the first six months of AI therapy.

Inclusion criteria:

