Data analysis: Preliminary Analyses. Exploratory analyses will be performed for data description and screening for anomalies (e.g., outliers, nonnormality). This will be done to: 1) describe univariate and bivariate distributions; 2) identify group imbalances and associations between dependent variables and suspected covariates/ confounders; 3) evaluate missing data; and 4) check for violation of statistical assumptions. If assumptions are violated, data transformations or more statistically robust procedures will be considered. Covariates/ confounders will be included in models secondarily and their effects on primary predictors/factors will be evaluated. The randomness of missing data will be investigated using available information on subject characteristics to help discern patterns in missing data, identify possible missing data mechanisms and inform strategies to handle missing data. If the data are ignorable missing, the estimation procedures to be used will produce unbiased estimates while allowing us to retain observations with missing values on the outcome variables. If needed, multiple imputation would be used to impute missing values on covariates. If the data are not ignorable missing, we may use selection or pattern mixture modeling to investigate the sensitivity of results.

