Analysis Plan for Aim 1. An "intent-to-treat" (ITT) approach will be used for data analysis. All subjects will be included in the groups to which they were assigned, regardless of adherence to protocol, treatment received, withdrawal or protocol deviation. Although this approach is recommended for efficacy analyses in Retaste sensitivity of the results assuming ITT will be explored using information collected regarding participant's adherence to the exercise intervention (e.g., protocol, amount of treatment received) as well as the amount of activity engaged in by the usual care group. The primary endpoint, changes in cognitive function, will be derived from normed (for age, education) composites of neuropsychological test scores (expressed as mean Z-scores).¹ (Table 2) The composite scores for the targeted cognitive function domains are empirically derived via exploratory factor analysis. Given the variation in scaling, test scores are converted to Z-scores related to an established cohort of age- and education-matched healthy women, and then averaged into composites, where negative scores indicate poorer cognitive function. Linear mixed-effects modeling with linear contrasts will be used to examine the effect of treatment assignment on cognitive function over time. When fitting models, time will be repeated within-subjects

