factor, while treatment assignment will be a between-subjects factor, with an interaction between time and group. Each derived cognitive domain composite will be modeled separately and interaction terms will be included to test our hypothesis that executive, memory, and attention domains will be more affected than other domains. We will consider baseline cognitive function values both as an assessment point and as a possible covariate in analyses. Fixed and/or time-dependent covariates may be included to adjust for group imbalances or variables related to the dependent variables. Standard fit indices will also be used to identify the most appropriate covariance structure. F-tests will test the main and interaction effects included in the model. Individual regression parameters will be computed and reported with standard errors to yield confidence intervals. For each model, residual analysis will be conducted to identify sources of model misspecification, outliers and influential observations. Sensitivity analyses will be performed to discern the impact of influential cases on results. To test specific hypotheses, linear contrasts will be specified and estimated in the repeated measures model to compare changes from follow-up to baseline values between groups. Wald t-statistics will be used to test each contrast. Marginal modeling with generalized estimating equations will also be used as it tends to be more robust to misspecification of the covariance structure and violations in normality assumptions. Results from each modeling approach will be compared via sensitivity analyses.

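### The Aim 1 and Aim 2 effect models may adjust for time-dependent covariates, with no bar on variables that exercise can change and no named primary model

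*Combined protocol and SAP*

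**What the plan says.** All references are to the combined protocol and SAP.

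- **Analysis Plan for Aim 1, covariates:** "Fixed and/or time-dependent covariates may be included to adjust for group imbalances or variables related to the dependent variables". None is listed. On baseline cognition the plan is undecided: "We will consider baseline cognitive function values both as an assessment point and as a possible covariate in analyses".
- **Analysis Plan for Aim 1, principle and contrast:** the analysis is intention-to-treat: "All subjects will be included in the groups to which they were assigned, regardless of adherence to protocol, treatment received, withdrawal or protocol deviation". The hypothesis test uses linear contrasts to "compare changes from follow-up to baseline values between groups".
- **Data analysis, Preliminary Analyses:** the data screen is meant, among other things, to "identify group imbalances and associations between dependent variables and suspected covariates/ confounders". Then: "Covariates/ confounders will be included in models secondarily and their effects on primary predictors/factors will be evaluated".
- **Analysis Plan for Aim 2:** the Aim 1 approach is reused for imaging metrics, inflammatory markers and symptoms, which are called intermediate outcomes.
- **Specific aims, Aim 3:** the trial will "explore whether the effects of exercise on cognitive function are mediated by" imaging metrics, inflammatory markers and symptoms.
- **Research activities, Assessments:** Time 1 is before randomization. Behavioral, blood, imaging, activity and fitness measures are taken at both Time 1 and Time 2.

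**The concern.** With two main timepoints, a covariate that varies over time enters the model with its Time 2 value, which is measured after randomization. The plan gives two reasons for including a covariate: imbalance between groups, or a relation to the outcome. A variable on the path from exercise to cognition would meet both if the trial's own hypotheses are right. A difference between arms in such a variable at Time 2 is then a consequence of treatment, and adjusting for it removes part of what Aim 1 is meant to measure. If the variable also shares unmeasured causes with cognition, conditioning on it adds a further bias.

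The plan's intention-to-treat statement does not guard against this. It fixes who is analysed and in which group, but says nothing about covariates. Every woman could be analysed as randomized while the group-by-time contrast estimated something other than the total effect of assignment. The primary endpoint is at stake, and so are the Aim 2 outcomes, which inherit the rule.

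**Working it through.** **No figure to reproduce.** The documents give up to 127 women per arm (Research activities, Participants) and equal allocation. They give no effect size, SD, alpha, power or dropout rate for that number. Apart from 127 and the 1:1 ratio, every input below is an assumption.

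**Step 1. Power by mediated share.** Assume a total effect of 0.35 SD of change, two-sided alpha 0.05 and no dropout. Power ≈ Φ(δ√(n/2) − 1.96), with √(127/2) = 7.969.

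- Nothing mediated: δ = 0.35; 0.35 × 7.969 − 1.96 = 0.829; power about 80%.
- 25% mediated through the adjusted covariate: δ = 0.75 × 0.35 = 0.2625; 2.092 − 1.96 = 0.132; power about 55%.
- 50% mediated: δ = 0.50 × 0.35 = 0.175; 1.395 − 1.96 = −0.565; power about 29%.

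**Step 2. Form of the bias.** With two timepoints the group-by-time contrast is the between-arm difference in change. Let M be the change in a time-dependent covariate, with unit variance within arm. Let a be the effect of exercise on M, b the effect of M on cognition, and u the loading of both on an unmeasured common cause. Regressing change in cognition on group and M gives M the coefficient b + u², so

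adjusted group effect = total effect − a(b + u²).

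If a = 0 the two agree. If a and the M coefficient have the same sign, the estimate is pulled down. If they have opposite signs it is pushed up: with a = −0.3 and b + u² = 0.3, 0.35 becomes 0.35 + 0.09 = 0.44.

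**Step 3. Simulation** (4,000 runs per row, 127 per arm, two-sided 0.05).

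| Total | a | b | u | Formula, adjusted | Simulated, adjusted | Rejection without M | Rejection with M |
|---|---|---|---|---|---|---|---|
| 0.35 | 0.3 | 0.3 | 0 | 0.26 | 0.261 | 80.0% | 56.7% |
| 0.35 | 0.5 | 0.3 | 0 | 0.20 | 0.200 | 79.0% | 37.0% |
| 0.35 | 0.5 | 0.5 | 0 | 0.10 | 0.100 | 79.2% | 15.6% |
| 0.35 | 0.5 | 0.3 | 0.4 | 0.12 | 0.118 | 79.7% | 16.7% |
| 0.35 | 0 | 0.3 | 0 | 0.35 | 0.348 | 78.5% | 82.0% |
| 0.35 | 0 | 0.3 | 0.4 | 0.35 | 0.348 | 79.2% | 87.5% |
| 0 | 0.3 | 0.3 | 0 | −0.09 | −0.090 | 4.8% | 11.4% |
| 0 | 0.5 | 0.3 | 0 | −0.15 | −0.151 | 5.2% | 23.1% |
| 0 | 0.5 | 0 | 0.5 | −0.125 | −0.125 | 5.2% | 17.2% |
| 0 | 0 | 0.3 | 0.4 | 0 | −0.001 | 4.2% | 4.2% |

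The first two rows have mediated shares of 0.09/0.35 = 26% and 0.15/0.35 = 43%, and bear out Step 1. In the null rows with a > 0, adjustment shifts the estimate against exercise. The row with b = 0 has neither a direct nor an indirect effect, so its 17.2% comes wholly from the shared cause.

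**The case against.** The strongest reply is that the plan already puts covariates second. The Preliminary Analyses text has them enter secondarily and has their influence on the main factors examined, and the Aim 1 text says only that they may be included. This implies that a model without covariates is fitted first, so a shift caused by adjustment should be visible. Aim 3 also undertakes to report total, indirect and direct effects, so a total effect would appear beside any direct effect. This limits the harm but does not remove it. No section says which Aim 1 model supplies the primary test, and covariates are identified from imbalances and associations seen in the data.

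Three stronger readings are tempting, and the documents do not support them:

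- **That the mediators will be Aim 1 covariates and the result will be biased.** No section names a mediator as an Aim 1 covariate, and none says that imbalance is assessed at Time 2. The text admits such variables; it does not select them.
- **That the adjusted estimate would usually be too small.** Size and direction depend on the paths (Step 2).
- **That the adherence analysis has the same fault.** The plan says that "sensitivity of the results assuming ITT will be explored using information collected regarding participant's adherence to the exercise intervention", but it specifies no comparison of adherers with non-adherers, so there is no stated method to criticise.

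**Conclusion.** The point holds as a defect in a stated rule, with conditional harm. The plan expressly permits covariates measured after randomization in its treatment-effect models, on selection criteria that its own intermediate variables could meet, and leaves the primary model unnamed. If a covariate affected by exercise were used in the model that carries the test, the estimate would not be the total effect of assignment.

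Under the assumed inputs, 25–50% mediation takes 0.35 SD to about 0.26–0.18 SD and power from about 80% to 55–29%. With a true total effect of zero, the rejection rate rose to 11–23% in the scenarios tried. Where exercise does not affect the covariate, there is no bias. These figures illustrate scale; they do not predict this trial, and no number in the documents changes because of them.

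**What to change.** 1. For the Aim 1 and Aim 2 treatment-effect models, strike the allowance for time-dependent covariates.
2. Name as primary the model whose covariates are all fixed before randomization: the baseline value of the outcome and the minimization factors. For brain morphology add intracranial volume, which the Neuroimaging section already specifies.
3. Reconcile the minimization factors first. The Statistical Plan lists two (age and baseline executive function), while the Randomization paragraph under Research activities adds a third, time since primary treatment.
4. Reserve Time 2 values of symptoms, biomarkers, imaging metrics and other intermediate variables for the Aim 3 mediation models.
5. Label any model with other post-randomization terms as a sensitivity analysis. This includes test-administration mode and the factors recorded before a blood draw, since both can arise after assignment.

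The cost is SAP wording; no new data are needed. The downside is some forgone precision. In the two simulated scenarios with a total effect of 0.35 SD and a covariate that exercise does not change, leaving it out cost about 3.5 and 8.3 percentage points of power (82.0% to 78.5%, and 87.5% to 79.2%). Prognostic baseline covariates may recover part of that.

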
populations and therefore submaximal vo_2 is often the desired method. This method has people walk at a slow - moderate pace with increasing grade increments up to the goal heart rate of 85% of the age-based maximum (220-age) or a rating of perceived exertion equal to or greater than 15 for those individuals whose heart rate response is blunted due to medication. This approach does not require the attendance of a physician because it is within the safe heart rate work zones and leads do not have to be attached to the participant. The submaximal vo_2 assessment usually takes about 15 - 30 minutes to complete depending on the starting fitness level of the participant. During the exercise test, heart rate is continuously monitored along with blood pressure readings every two minutes. The blood pressure is obtained by the Sentech Tango 2 automated unit. This blood pressure unit is designed for exercise testing and has been tested as a valid and reliable system to measure blood pressure during exercise. When the subject reaches the endpoint goal of the exercise test, the mouthpiece and head gear will be removed and they will undergo a four minute active cool-down in which they will walk at a slower rate with zero incline grade. After these four minutes the participant will be helped off of the treadmill and undergo a passive cool-down session in which they are seated in a chair. The participant's heart rate and blood pressure will be continuously monitored through the cool-down period and the participant will not be allowed to leave until the vital signs return to normal patterns. Blood pressure will also be monitored both before and after the fitness test to ensure that changes in blood pressure resulting from exercise are all normal. If the participants vital signs remain elevated after a cool down and rest period, the study physician will be called and will provide instructions for further monitoring of the participant. Situations like this are very rare and occur in less than 1/10,000 instances of fitness testing. These assessments will be conducted in [name] laboratory by an exercise physiologist with >15 years of coaching and exercise testing who is AED and Recertified and has certifications in exercise physiology from the American College of Sports Medicine. Prior to engaging in exercise, participants may be fitted with one or two physical activity monitoring devices (Body Media Sense Wear mini armband or Autographing). The Body Media Sense wear Armband is worn around the upper left arm. Hectograph Link is a wristband worn on the non-dominant arm. Both devices will record physiological data (e.g., heat flux, sweat rate, etc.) over the duration of their exercise test; this information is used in an algorithm to determine intensity and amount of physical activity. The participants will be provided with detailed instructions regarding wearing of the device(s) as well as the option to remove the device(s) if it becomes problematic. Participants may also be asked to wear the physical activity monitoring device(s) for a week before or after the exercise testing session. This way we can get a more comprehensive idea of both activity and fitness levels. In addition, all participants, regardless of group assignment, will be asked to wear the device(s) 3 additional times through their participation in this study(approximately every 5 weeks) and again at the follow-up assessment (TP2) for total of 5 times over the course of participation in the study. Participants who wear the Actigraphy Link will be given a log at the time they receive their device. This log is used to report any time/reason the device is removed as well as information about their sleep. The self-report information contained in the log will be compared to and used in interpreting the device data. Alternatively, in the event that a participant cannot come to Sennott Square for this testing for any reason (e.g., preference, weather, pandemic-related restrictions.), a brief heart-rate monitoring session may take place virtually either by phone or teleconferencing. During this guided session, the participant will be asked to wear study-provided heart rate monitor for approximately 5 minutes and asked to report readings to study staff. Participants will also be asked to report their weight; home scale may be provided for participants to use (with instructions to return via pre-paid mailer when complete). Data from the session can provide information to estimate results from a VO_2 test. Participants may also be asked to complete questionnaires regarding exercise knowledge and self-efficacy during the physical activity and fitness assessment, time permitting. Alternatively, these may be included in the behavioral assessment. The behavioral assessment includes a battery of standard clinical neuropsychological tests that assess verbal ability, visuospatial ability, attention/processing speed, memory, and executive function, will be administered. These tests have standard administration protocols and will be administered by trained staff. This is expected to take approximately 90 minutes. We will also administer measures of demographics, mood and quality of life. The tasks and measures will include those listed in section 2.8. All of the tests will be identified by the subject ID and not by name. At times these tests can be mentally fatiguing or frustrating. Subjects will be told that the tests are designed to be challenging and that they should just perform to the best of their abilities. They will also be offered breaks as needed between tests to help reduce fatigue and frustration. Data collected will be transported by the research personnel immediately following the assessment if conducted in the participant's home to the office of the PI in the

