Analysis Plan for Aim 2. We will use the same analytical approach described for Aim 1 to fit models for intermediate outcomes (neuroimaging metrics of brain health, inflammatory markers, and symptoms) and to test Aim 2 hypotheses regarding the effects of exercise on primary intermediate outcomes (neuroimaging metrics and inflammatory markers of IL-6 and CRP). The only difference will be that initial neuroimaging analyses will be conducted on a voxel-wise basis using FSL, SPM, treasuer, depending on the imaging modality and analysis (e.g., volumetric). In addition to voxel-wise analyses we may apply regions-of-interest (ROI) analyses since our primary hypotheses focus on prefrontal and hippocampal regions. Thesaurus can be generated using anatomical templates from normalized MNI space or from functionally-derived estimates of activation or connectivity. We will use standard cluster-based corrections for multiple comparisons of fMRI results, threshold-free cluster enhancement, and an FDR of $p < .01$ for volumetric and white matter analyses.

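### The primary endpoint is several separately tested cognitive composites with no success rule or multiplicity control, so the false-positive rate for Aim 1 is not controlled

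*Combined protocol and SAP*

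**What the plan says.** The Analysis Plan for Aim 1 names one endpoint but builds it from plural composites: "The primary endpoint, changes in cognitive function, will be derived from normed (for age, education) composites of neuropsychological test scores". The number of composites is not fixed in the text, because "The composite scores for the targeted cognitive function domains are empirically derived via exploratory factor analysis". A Table 2 is cited there but is not in the text available to me, and I draw nothing from its absence.

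The behavioural battery under Research activities, Assessments, covers five domains: "verbal ability, visuospatial ability, attention/processing speed, memory, and executive function". Hypothesis 1, under Specific aims, expects that "attention, executive and memory functions will be influenced more than other domains".

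On testing, the same section states "Each derived cognitive domain composite will be modeled separately" and then "Wald t-statistics will be used to test each contrast". It gives no alpha, no sidedness, no order of testing and no adjustment across composites. It also does not say how many composites must show an effect for Aim 1 to succeed. The plan's only multiplicity provision is in the Analysis Plan for Aim 2 and concerns imaging: "We will use standard cluster-based corrections for multiple comparisons of fMRI results, threshold-free cluster enhancement", with a false discovery rate threshold for the volumetric and white matter analyses.

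**The concern.** Aim 1 asks whether exercise improves cognitive function, and the plan answers with a set of separate tests. Nothing says what pattern of results counts as success. One nominally significant composite out of several could be presented as a positive primary result, and the plan has no rule against it. The F-tests for group and time sit inside each single-composite model, so they control nothing across composites. The authors provided for multiplicity in imaging but wrote no counterpart for the primary aim.

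**Working it through.** The documents give no alpha, family-wise error rate or power calculation for Aim 1, so there is no figure of the plan's own to reproduce.

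**Inputs**
- Number of composites, k: 5 (domains in the Assessments section) or 3 (domains named in Hypothesis 1).
- Per-test level: two-sided 0.05, critical value c = 1.96. This is an assumption.
- Correlation between the domain test statistics, ρ: equal for all pairs, 0 to 0.8. This is an assumption.
- Arm size: up to 127 (Research activities, Participants). Used only for the cost of the fix.

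**Chance of at least one false significant result when exercise has no effect on any domain**

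For independent tests, the rate in either direction is 1 − 0.95^k and the rate in favour of exercise is 1 − 0.975^k:
- k = 5: 1 − 0.95^5 = 22.6%; 1 − 0.975^5 = 11.9%.
- k = 3: 1 − 0.95^3 = 14.3%; 1 − 0.975^3 = 7.3%.

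For equally correlated normal statistics, the rate is 1 − ∫ [Φ((c − √ρ·u)/√(1−ρ)) − Φ((−c − √ρ·u)/√(1−ρ))]^k φ(u) du. The second Φ term is dropped for the direction favouring exercise.

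| ρ | 5 composites, either direction | 5 composites, favouring exercise | 3 composites, either direction | 3 composites, favouring exercise |
|---|---|---|---|---|
| 0 | 22.6% | 11.9% | 14.3% | 7.3% |
| 0.3 | 20.9% | 10.5% | 13.6% | 6.8% |
| 0.5 | 18.3% | 9.2% | 12.5% | 6.3% |
| 0.7 | 14.8% | 7.4% | 10.9% | 5.5% |
| 0.8 | 12.7% | 6.4% | 9.8% | 4.9% |

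A single test gives 5% in either direction and 2.5% in favour of exercise. For ρ from 0.7 to 0, the favourable-direction rate is therefore inflated about 3.0 to 4.8 times with five composites (7.4/2.5 to 11.9/2.5) and 2.2 to 2.9 times with three (5.5/2.5 to 7.3/2.5).

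**After correction**

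With three composites at 0.05/3 = 0.0167 each, which is Holm's first step, the either-direction rate is 4.9% if independent and 4.5% at ρ = 0.5.

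**Cost in detectable effect**

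By normal approximation, 80% power, n per arm: d = (z for alpha + 0.842) × √(2/n), with z = 1.960 at 0.05 and 2.394 at 0.0167. The SD is that of the quantity compared between arms.
- n = 127: 2.802 × 0.1255 = 0.35; 3.236 × 0.1255 = 0.41.
- n = 114 (assumed 10% loss): 2.802 × 0.1325 = 0.37; 3.236 × 0.1325 = 0.43.
- n = 102 (assumed 20% loss): 2.802 × 0.1400 = 0.39; 3.236 × 0.1400 = 0.45.

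**The case against.** The best defence is that Hypothesis 1 predicts a pattern: three domains affected more than the rest, with interaction terms planned to test it. One isolated significant domain, such as visuospatial ability, would not support that hypothesis. This stands as far as it goes. But the hypothesis concerns relative effects, and it does not declare the three domains the primary family or say how many must succeed. Even a family of three, tested without adjustment, carries an either-direction rate of 11-14%.

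A reader might also infer more than the documents support:
- **That a false claim of benefit has a 15-23% chance.** That range counts significant differences in either direction, including harm. The rate favouring exercise is about half of it, and its comparator is 2.5%, not 5%. It would reach 22.6% for five independent tests only if each were one-sided at 0.05, which the plan does not say.
- **That the plan breaks its own 5% level.** It states no level for Aim 1, so 0.05 is my assumption.
- **That there are at least five primary composites.** The list of five describes the battery. Factor analysis sets the composites, and Table 2 may list them.
- **That the choice between the mixed model and generalized estimating equations is a further uncontrolled test.** The plan names the mixed model for the treatment effect, adds the other method and says "Results from each modeling approach will be compared via sensitivity analyses". That is adequate.

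**Conclusion.** The concern holds in this form: Aim 1 has a multi-part primary endpoint, each part tested separately, with no decisive composite, success rule or error control. If any one significant composite counts as success, the chance of at least one false significant difference is about 15-23% for five composites and 11-14% for three. In favour of exercise it is about 7-12% and 5.5-7.3%.

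These figures assume two-sided 0.05 per test, equal correlations of 0.7 to 0 and no true effect in any domain. Higher correlations lower the rates and more composites raise them. The gap itself is certain from the text, while its exact size is not. The data remain usable, so this is a change that should be made rather than a fatal flaw.

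**What to change.** Before outcomes are compared by arm, amend the Analysis Plan for Aim 1 to:
1. State a family-wise alpha of two-sided 0.05.
2. Define the primary family as the composites for attention, executive function and memory, and fix in advance how the factor-analysis results map to those three. The mapping is needed because the factor analysis may not give exactly one composite per domain.
3. Test the group-by-time contrasts at TP2 from the mixed model, with Holm across the three.
4. Report the remaining domains as secondary, with confidence intervals.

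A single named primary composite or one global test would also control the error. Holm on three fits Hypothesis 1 most closely.

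The change is to SAP wording only, but it costs some sensitivity. At Holm's strictest step the effect detectable with 80% power rises from about 0.35 to 0.41 SD if all 127 per arm contribute data. Since 127 is a ceiling, that is the best case. With an assumed 10-20% loss the rise is from 0.37-0.39 to 0.43-0.45 SD. Later Holm steps use larger thresholds and cost less.
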